7.3.1 Subject Withdrawal from the Study

A subject *must* permanently discontinue study drug treatment and *must* be withdrawn from the study prematurely for any of the following reasons:

The subject becomes pregnant. Treatment must be *immediately* discontinued. The pregnancy must be reported to the study center (study coordinator/treating physician/PI) immediately. Information about the subject, the subject's pregnancy, the outcome of the pregnancy, and the status of the infant at 8 to 12 weeks of age will also be collected.

The subject desires to discontinue study drug treatment under this protocol. Patients have the right to withdraw from the study at any time and for any reason. The investigator also has the right to withdraw patients from the study in the event of an intercurrent illness, non-compliance after a prescribed procedure, protocol violations, administrative reasons, other reasons.

The subject receives or wishes to start any restricted medication listed in table 2 except corticosteroids.

At the discretion of the investigator for medical reasons or for non-compliance.

The study will be prematurely terminated for an individual if an exclusion criteria occurs during the study.

Dosing in stage 1 has to be discontinued in case of a SAE. If dosing is stopped for greater than 2 weeks, the study medication will be stopped in that patient and the patient will be withdrawn prematurely from the study.

The reasons for discontinuation of the study drug must be recorded in the subject's Clinical Center patient file and the respective case report forms (CRFs).

Patients discontinuing dosing will be followed for an additional 2 months. If discontinuation was because of a serious adverse event, the patient will be followed until the event is resolved or stabilized, but not shorter than 2 months.

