7.2 Dose Titration Scheme

The dose unit for the following titration scheme has been set as 400 mg/capsule. Dosing is at morning, midday and evening with at least 6 hours between doses.

BOSWELAN will be titrated up to the highest well tolerated dose or to a maximum of 3 x 1600mg during Stage 1.

The dose titration period will be up to 28 days. The dose reached at that time point should be the maximum dose that is well tolerated.

Titration scheme: The dose unit has been set as 400 mg/capsule.

Days	Dosing schedule	Special measures
0	1-0-0	
1:	1-1-1	phone contact on Day 1 before morning dose
2-3	1-1-2	
4-6:	2-1-2	phone contact on Day 4 before morning dose
7-9:	2-2-2	
10-12:	2-2-3	
13-15:	3-2-3	phone contact on day 13 before morning dose
16-18:	3-3-3	
19-21:	3-3-4	
22-24:	4-3-4	
25-28:	4-4-4	

It is expected that adjustments to this schedule will be needed in the event that side effects occur or if dose reductions are necessary. However, patients should remain on each new dose for a minimum of 3 days before the next increase.

Any re-increase of dose after a dose reduction due to an adverse event requires consultation by phone with either the treating physician or the study nurse. In case of a serious adverse event (SAE), dosing will be stopped until the SAE has resolved. Dosing will then resume at a reduced dose level. If dosing is stopped for greater than 2 weeks, the study medication will be stopped in that patient and the patient will be withdrawn prematurely from the study.

Any intolerance of moderate or severe degree must be reported by the patient to either to the treating physician or a study nurse by phone.

The first dose will be administered in the respective Clinical Center. Each patient will contact the study nurse on days 1 (before morning dose), 4 (before morning dose), and on day 13 (before morning dose). Patients will be seen at the center

on days 0 and day 28 and the morning dose will be administered at the center on these days (in case of participating in the pharmacokinetic sub-study).

Treatment of adverse events is at the investigator's discretion.

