7.5.3 Treatment of Relapses on Scheduled or Unscheduled Visits

Patients having a clinically significant relapse/exacerbation will be treated according to the recommendations of the German society for neurology (DGN) with 1000 mg methylprednisolone, given once a day via i.v. infusion for 3 days unless there are valid reasons for not treating or for alternative schedules. In case of a relapse each patient has to give written informed re-consent before continuing the study irrespective of his/her choice to receive methylprednisolone. In the case of methylprednisolone administration, a subsequent MRI examination will be postponed for at least 28 days, while treatment with BOSWELAN and study visits will be continued according to the study protocol.

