In case of a fatal or life threatening SUSAR the Sponsor will report all information relevant for judging the event immediately, at the latest 7 days after the event becomes known to the relevant Ethics Committees and the relevant Competent Authorities, as well as to all Investigators involved in the trial and the DSMB.

The Sponsor will further report immediately, at the latest 15 days after it becomes known, all circumstances that require a revision of the risk-benefit analysis of the investigational product to the above mentioned authorities. This especially includes:

- Singular cases of expected severe adverse events with an unexpected outcome
- Increased incidence of expected severe adverse events that are judged as being clinically relevant
- SUSARs which occur after termination of the clinical trial (max. 2 weeks after termination or exclusion)
- Events related to study procedures or development of the study medication, which could affect a subject's safety

The Sponsor will once a year submit the annual safety report to the Competent Authority(ies).

All person-related data will always be transmitted pseudonymised. Before reporting a SUSAR the subject will be unblinded.

Exception rules for the reporting:

In this clinical trial the following Serious Adverse Events are excluded from reporting:

- Severe or unexpected events which occur after screening or enrolment, but before first application of the investigational drug
- Hospital admissions for the purpose of diagnostic or therapeutic purposes which were planned before study inclusion
- Expected serious events, which could occur because of the administration of the investigational product and represent known effects of the investigational product.
- Hospital admissions for the purpose of treating a relapse

Table 3. Adverse Event Definitions

Serious Adverse Event	
Serious adverse events are defined as the following:	

 ▪ Any death. ▪ Any life-threatening* event, i.e., an event that places the subject, in the view of the investigator, at immediate risk of death from the event as it occurred (does not include an event that, had it occurred in a more severe form, might have caused death). ▪ Any event that requires or prolongs in-patient hospitalization. ▪ Any event that results in persistent or significant disability/invalidity. ▪ Any congenital anomaly/birth defect diagnosed in a child of a subject who participated in this study and received study drug. 	

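### For a stage 1 SAE that resolves within 2 weeks, Section 7.3.1 withdraws the patient and Section 7.2 resumes dosing; whether relapse admissions follow the SAE dosing rule is not stated

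*Protocol*

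**What the plan says.** Five places in the protocol bear on dosing after a serious adverse event.

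- **Section 7.3.1, lead-in.** For each listed reason the subject must "permanently discontinue study drug treatment" and must "be withdrawn from the study prematurely for any of the following reasons".
- **Section 7.3.1, SAE entry.** One entry in that list is "Dosing in stage 1 has to be discontinued in case of a SAE". It is followed directly by "If dosing is stopped for greater than 2 weeks, the study medication will be stopped in that patient", with premature withdrawal as the consequence.
- **Section 7.2, Dose Titration Scheme.** For the titration period of up to 28 days, which is stage 1: "dosing will be stopped until the SAE has resolved. Dosing will then resume at a reduced dose level". The same 2-week limit then follows.
- **Section 7.5.3.** When methylprednisolone is given for a relapse, the next MRI is postponed, "while treatment with BOSWELAN and study visits will be continued according to the study protocol".
- **Section 12.1 and Table 3.** Table 3 counts an event that leads to or prolongs an in-patient stay as serious. The list of serious events exempt from reporting includes "Hospital admissions for the purpose of treating a relapse".

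**The concern.** Sections 7.2 and 7.3.1 cover the same event in the same stage. One reads as a temporary stop followed by re-dosing, the other as a permanent stop with withdrawal. This is a multicentre, open-label trial, so two sites that each follow the protocol could handle the same patient in opposite ways.

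Three things depend on the answer:

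- **Re-exposure.** The two rules differ on whether a patient receives the drug again after an SAE.
- **The safety tables.** Safety and tolerability is the primary objective (Sections 3.1 and 13.3). Section 13.3.1 identifies adverse events that led to stopping treatment or lowering the dose. The same SAE is the first kind under the 7.3.1 lead-in and the second kind under 7.2.
- **The analysis sets.** The Summary seeks at least 30 subjects completing 8 months of treatment, and the primary efficacy comparison uses months 5 to 8. A patient withdrawn in stage 1 contributes to neither. A patient who resumes may contribute to both, provided the dose condition of at least 800 mg t.i.d. is met.

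**Working it through.** The plan gives no figure for this point, so the check is to apply each rule as written to each type of event.

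1. **Stage 1 SAE, not a relapse, dosing stopped for 2 weeks or less.** The lead-in of 7.3.1 together with its SAE entry gives permanent discontinuation and withdrawal. Section 7.2 gives resumption at a lower dose once the event has resolved. These are two incompatible outcomes. The 2-week sentence in 7.3.1 sides with 7.2: if every stage 1 SAE already meant withdrawal, a separate time limit would have nothing to do. Section 7.3.1 therefore conflicts with 7.2 through its lead-in, and its own second sentence conflicts with that lead-in.
2. **Stage 1 SAE, not a relapse, dosing stopped for more than 2 weeks.** Both sections lead to withdrawal. There is no conflict.
3. **Relapse treated without admission and not otherwise serious.** No SAE rule is triggered. Section 7.5.3 continues drug where methylprednisolone is given. There is no conflict.
4. **Stage 1 relapse that is both hospitalised and treated with methylprednisolone.** Table 3 makes it an SAE. Section 12.1 takes it out of reporting but still calls it a serious adverse event, and nothing takes it out of the SAE dosing rules. Section 7.5.3 continues drug after methylprednisolone, but it does not mention admission and it refers back to the protocol. The governing rule is not stated.

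**How often case 4 could arise.** The protocol gives neither a relapse rate nor an admission rate. Assume 0.5 to 1.0 relapses per patient-year, with 10% to 50% of relapses admitted. The conflicting SAE texts concern stage 1, so the exposure is 28 days in 30 patients:

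- patient-years: 30 × 28/365 = 2.30
- relapses: 2.30 × 0.5 = 1.15, to 2.30 × 1.0 = 2.30
- relapse admissions: 1.15 × 0.10 = 0.1, to 2.30 × 0.50 = 1.2

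**Weight of one patient.** One withdrawal among the planned 30 completers is 1/30 = 3.3%.

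**The case against.** The best defence treats the SAE entry in 7.3.1 as a single two-sentence item: stop on an SAE, and withdraw if the stop exceeds 2 weeks. Its second sentence matches the corresponding one in 7.2, so the item may simply restate 7.2 and have been placed under an unsuitable lead-in. Further, both sections stop dosing at once on an SAE, and 7.3.1 lets the investigator withdraw a patient for medical reasons, so nobody is forced to re-dose. The protocol also reports no serious adverse events in more than 500 treated patients (Sections 2.5.1 and 15), so few cases are to be expected.

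Much of this is fair. It makes the intent of 7.2 a plausible reading and keeps the expected count low. It does not remove the conflict, because the lead-in is mandatory and covers each listed reason. The closing paragraph of 7.3.1 also sets follow-up for patients who discontinued because of an SAE, which fits either reading. A site could defend either course from the text.

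A reader might go further in four ways that the documents do not support.

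- **That any SAE in titration has three dosing outcomes.** It has two. A third appears only for case 4, and only by combining 7.5.3 with Table 3 and the reporting exemption. No passage instructs that dosing continue through a relapse admission.
- **That the individual stopping rules in 7.3.2.1 add another conflict.** The relapse and EDSS criteria there are presented as additional grounds for stopping. They do not require that a patient with one relapse stay on drug.
- **That all stage 1 SAEs are affected.** Those with a stop of more than 2 weeks are treated alike in both sections.
- **That relapse admissions over the full 8 months should be counted.** That period is about 8.7 times the relevant one (243/28 days), because the 7.3.1 entry names stage 1 and the 7.2 rule sits in the titration scheme.

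**Conclusion.** The point stands as an internal inconsistency. For a stage 1 SAE that resolves within 2 weeks, the protocol gives two instructions that cannot both be followed, and 7.3.1 contradicts its own lead-in. This rests on the text alone and needs no assumed rate.

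The number of events is probably small. The consequence for each is not: it decides re-exposure or withdrawal, the row of the safety table in which the event is counted, and whether the patient can still be one of the 30 completers. It should be corrected.

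The relapse-admission question is a linked but lesser ambiguity. On the assumed rates it concerns about 0.1 to 1.2 events in stage 1. Which clinical rule is right is not judged here.

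**What to change.** Amend Sections 7.2 and 7.3.1 so that the lead-in, the SAE entry and the 2-week sentence together give one consistent consequence for a stage 1 SAE. State whether a hospitalised, steroid-treated relapse falls under the SAE dosing rule or under Section 7.5.3. Use the same rule in Section 13.3.1 when an adverse event is classed as leading to discontinuation or to dose reduction. The sponsor and the DSMB choose the rule.

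The cost is amendment wording only, with no added visits, patients or procedures.

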7.3.2 Stopping Rules for Individual Patients and for the Study

7.3.2.1 Stopping Rules for Individual Patients

MRI Safety Criteria

Regarding stopping rules, we apply stipulations that we have previously applied in other trials of this kind (39, 40). Dosing will be discontinued in patients showing an increase in total Gd-enhancing lesions beyond 6 standard deviations of the mean lesion frequency during baseline plus 10 lesions. The maximum lesion number allowed, before treatment will be stopped, is 40 Gd-enhancing lesions. The upper margin (40 Gd-enhancing lesions) stems from a systematic review of the numbers and distribution of contrast-enhancing lesions derived from the placebo cohorts of pivotal phase III trials, which was performed by the Sylvia Lawry Center for MS Research ([name] and colleagues). Furthermore, if in the opinion of the investigators there is a change in appearance of enhancing lesions inconsistent with the patient's previous MRIs, e.g. change in average lesion size from small to substantially larger lesions, dosing will be discontinued.

Clinical Safety Criteria

Two clinical safety criteria will also be used as stopping criteria for each individual patient:

Clinical criterion 1 - relapses: Two or more confirmed relapses/exacerbations. A relapse/exacerbation is defined as the appearance of any new symptom or worsening of previous symptoms associated with significant changes in signs lasting longer than 24 hours and not accompanied by a rise in temperature or infection ("pseudoattack" modified after Schumacher (51)).

Single paroxysmal events (such as a tonic spasm) do not constitute a relapse, but multiple episodes occurring over not less than 24 hours do.

Treatment of relapses will be conducted according to the recommendations of the German Neurological Society (DGN)(section 7.5.3).

or

Clinical criterion 2 - progression: Worsening of two or more points on the EDSS scale for 3 months during the treatment phase, compared to baseline in the first 3 months before treatment. For patients with an EDSS score of 5.5 at study entry, a worsening of one point on the EDSS scale for 3 months during the treatment phase will lead to halt of study treatment.

Patients, who discontinue study medication due to one of the above mentioned stopping rules, will be advised to start on one of the established disease-modifying treatments according to the recommendations of the German Neurological Society (DGN).

7.3.2.1 Stopping Rules for the Study

MRI Safety Criteria

The trial will be put on hold if the following MRI safety concerns arise:

1. Increase in total CELs beyond 6 standard deviations, plus 10 lesions, of the individual mean lesion frequency during baseline. This criterion applies to patients with low baseline inflammatory MRI activity.
2. The maximum number of new lesions allowed at one MRI exam in an individual patient before the trial will be put on hold is 40 lesions.
3. If in the opinion of the investigators, there is occurrence of atypical non MS-like lesions or MRI lesions that are unusual for the individual patient dosing will be discontinued and the patient will be prematurely withdrawn from the study. The latter consideration is up to the judgement of the trial neuroradiologist and, if such concerns should arise, will be discussed with the DSMB within 48 hours of the respective MRI scan.

Clinical Safety Criteria

The entire trial will be put on hold if the following clinical safety concerns occur:

1. Relapses: Two or more relapses/exacerbations during the treatment phase (stage 1-3) in the first 3 months post treatment in more than 1 of the first 4 participants, more than 2 of the first 8 participants, and 3 or more participants in the entire group.
2. Progression: Worsening of two or more points on the EDSS scale, during the treatment phase, compared to baseline in the same number of patients as under (1). The change in EDSS must be confirmed and consistent through three monthly visits.
3. All serious adverse events and adverse events will be reported within 3 months to the data safety monitoring board (DSMB), which will decide on the discontinuation of the study.

If dosing had to be discontinued in five patients because of MRI parameters or in the number of patients as in 1 of clinical safety criteria because of clinical parameters the study will be placed on clinical hold, i.e. treatment with BOSWELAN of all patients already in the study will be discontinued and no additional patients will be recruited until the data from the trial has been reviewed by the DSMB.

If any safety issue leads to concerns to continue treatment with BOSWELAN in the MS or CIS patients of this study or if any safety issue of other clinical studies with BOSWELAN raises such concerns, the study will be put on hold or be terminated. The study DSMB will review the safety and efficacy data on a regular basis.

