Dosing will be discontinued in patients showing an increase in total Gd-enhancing lesions beyond 6 standard deviations of the mean lesion frequency during baseline plus 10 lesions. The maximum lesion number allowed during treatment will be 40 Gd-enhancing lesions. The upper margin (40 Gd-enhancing lesions) stems from a systematic review of the numbers and distribution of contrast-enhancing lesions derived from the placebo cohorts of pivotal phase III trials, which was performed by the Sylvia Lawry Center for MS Research ([name] and colleagues). Furthermore, if in the opinion of the investigators there is a change in appearance of enhancing lesions inconsistent with the patient's previous MRIs, e.g. change in average lesion size from small to substantially larger lesions, dosing will be discontinued.

Two clinical safety criteria will also be used as stopping criteria:

Clinical criterion 1- relapses: Two or more confirmed relapses/exacerbations (see section 7.3.2 for definition of relapse/exacerbation) or clinical criterion 2 - progression: Worsening of two or more points on the EDSS scale during the treatment phase, compared to baseline post treatment, confirmed and consistent through three monthly visits.

If dosing had to be discontinued in five patients because of MRI parameters or in more than 1 of the first 4 participants, more than 2 of the first 8 participants, and 3 or more participants in the entire group because of clinical parameters the study will be placed on clinical hold, i.e. treatment with BOSWELAN of all patients already in the study will be discontinued and no additional patients will be recruited until the data from the trial has been reviewed by the safety committee.

Side effect monitoring, blood biochemistry (especially liver enzyme levels), as well as neurological and other clinical parameters will be used to further assess safety.

Efficacy

Parameters:

Primary outcome measure

- Number and volume of total Gd-enhancing lesions

Secondary outcome measures

- Number of persisting Gd-enhancing lesions
- Number of new active lesions (new Gd-enhancing lesions +new or enlarging non-enhancing T2 lesions)
- Number of new Gd-enhancing lesions evolving into persistent hypointense lesions
- T2 lesion volume
- T1 hypointense lesion volume
- Number of persisting T1 lesions
- Brain atrophy (brain parenchymal fraction)
- Magnetization Transfer Ratio (MTR)
- Relapse rate

Tertiary outcome measures

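### The MRI rule for holding the trial differs between texts: section 7.3.2 holds on one patient with more than 40 new lesions, while the synopsis holds only after five MRI discontinuations

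*Protocol*

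**What the plan says.** Protocol section 7.3.2 contains two blocks, both numbered 7.3.2.1: one for individual patients and one for the study.

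- **Study rules, item 1.** Under a lead-in that holds the trial if the listed concerns arise: "Increase in total CELs beyond 6 standard deviations, plus 10 lesions, of the individual mean lesion frequency during baseline". The next sentence confines this criterion to patients whose baseline MRI activity was low, without defining low. No number of patients is given.
- **Study rules, item 2.** This fixes a ceiling: the "number of new lesions allowed at one MRI exam in an individual patient before the trial will be put on hold is 40 lesions".
- **Study rules, item 3.** For atypical lesions, or lesions unusual for that patient, "dosing will be discontinued and the patient will be prematurely withdrawn from the study". Such concerns go to the DSMB within 48 hours of the scan.
- **Study rules, closing paragraph.** "If dosing had to be discontinued in five patients because of MRI parameters", the study goes on clinical hold. This is defined as stopping BOSWELAN in everyone and closing recruitment until the DSMB has reviewed the data.
- **Individual rules.** The 6 SD plus 10 limit appears without the low-activity restriction, followed by "The maximum lesion number allowed, before treatment will be stopped, is 40 Gd-enhancing lesions". A marked change in lesion appearance also stops dosing.
- **Synopsis (section 1, stopping rules).** "The maximum lesion number allowed during treatment will be 40 Gd-enhancing lesions", as a limit for the individual patient. The study-level rule begins: "If dosing had to be discontinued in five patients because of MRI parameters or in more than 1 of the first 4 participants". There is no hold triggered by one patient's MRI.

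**The concern.** The same section gives two different patient counts for an MRI-based hold of the whole trial, one and five, and the synopsis carries only the larger. Item 1 adds a third case, a hold criterion with no count at all. The relapse and EDSS rules beside it do give patient counts, so the gap stands out.

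The primary objective is safety and tolerability, and section 3.1 names the mean total number of Gd-enhancing lesions as the primary MRI safety parameter. If a hold has the meaning defined in the closing paragraph, an error in either direction is costly. Treatment and recruitment could stop when no hold was intended, or continue when the section required a stop. Investigators and the DSMB need one answer before the first such scan arrives.

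**Working it through.** The hold count is a fixed rule, so there is no figure of the plan's own to reproduce. The check sets the texts side by side and works out where item 1 takes effect.

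**1. The texts side by side**

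| Event in one patient | Study rules, items 1–2 | Closing paragraph and synopsis |
|---|---|---|
| 41 new lesions at one exam | Trial held (item 2) | No hold; at most 1 of the 5 needed |
| Beyond 6 SD plus 10, low baseline activity | Trial held on a literal reading (item 1, no count) | No hold; 1 of 5 |
| Beyond 6 SD plus 10, baseline activity not low | Not covered by item 1 | 1 of 5 |
| More than 40 Gd-enhancing lesions in total, 40 or fewer of them new | Not covered by item 2 | 1 of 5 |
| Changed lesion appearance | Patient withdrawn, DSMB discussion (item 3) | 1 of 5 |

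In the first row, the patient counts toward five only if dosing is stopped under the individual limit, which refers to Gd-enhancing lesions. Item 2 does not say whether its new lesions are Gd-enhancing. Elsewhere the protocol also counts new non-enhancing T2 lesions (section 3.2), so the doubt is real.

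**2. Where item 1 takes effect at the entry minimum**

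Input: section 5.3 requires an average of at least 0.5 Gd-enhancing lesions over the baseline period, which has 4 MRIs. The minimum is therefore 0.5 × 4 = 2 lesions, so the four counts in some order are 1,1,0,0 or 2,0,0,0. If any treated patient has low baseline activity, this one does.

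Formula: limit = mean + 6 × SD + 10. The protocol does not give the SD divisor, so both are shown.

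- Counts 1,1,0,0: the squared deviations sum to 4 × 0.25 = 1.
  - Divisor n−1: SD = √(1/3) = 0.577; limit = 0.5 + 3.46 + 10 = 13.96; first count beyond it is **14**.
  - Divisor n: SD = √(1/4) = 0.500; limit = 0.5 + 3.00 + 10 = 13.50; first count **14**.
- Counts 2,0,0,0: the squared deviations sum to 2.25 + 3 × 0.25 = 3.
  - Divisor n−1: SD = √(3/3) = 1.000; limit = 0.5 + 6.00 + 10 = 16.50; first count **17**.
  - Divisor n: SD = √(3/4) = 0.866; limit = 0.5 + 5.20 + 10 = 15.70; first count **16**.

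Leaving the mean out (6 SD + 10) gives limits of 13.46, 13.00, 16.00 and 15.20, with the same first counts. For such a patient the missing count in item 1 matters from 14 to 17 lesions, well below 40.

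**3. Does the five-patient rule have work of its own?**

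Take assumed baseline counts of 1,3,5,3. The mean is 3 and the squared deviations sum to 8. With divisor n−1, SD = √(8/3) = 1.63 and the limit is 3 + 9.80 + 10 = 22.80. Dosing stops at 23 lesions under the individual rule. If this baseline is not low, item 1 does not apply, and the patient counts only toward five. The five-patient rule is therefore not redundant.

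**The case against.** The strongest defence is that these are separate triggers, any of which suffices. A stepped scheme makes sense: a high total count stops the patient, an extreme burst of new lesions in one patient stops the trial, and an accumulation of five discontinuations also stops it. A synopsis may abbreviate, and the fuller section is the stricter text, so the ambiguity leans toward caution. Individual dosing stops and the clause allowing a hold for any safety concern apply on every reading.

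Much of this stands. The texts do not strictly contradict each other. A reader might infer that items 1 and 2 leave the five-patient rule with almost nothing to do, but the documents do not support that. Item 1 is confined to low baseline activity and item 2 to new lesions. The five-patient rule therefore still covers 6 SD plus 10 stops in other patients, patients above 40 in total but not in new lesions, and changes in lesion appearance. It is also fair that item 3 is more than a patient withdrawal, since it requires prompt DSMB discussion, and that the meaning of a hold is spelled out only in the closing paragraph.

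The defence does not restore the missing trigger to the synopsis. Leaving out a rule that holds the whole trial changes what its reader would do. Nor does the defence supply a patient count for item 1 or say what low activity means.

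**Conclusion.** The point holds as an inconsistency in a decision threshold, and it should be fixed. After one patient with 41 new lesions at one exam, section 7.3.2 holds the trial and the synopsis does not: one patient against five. On a literal reading, item 1 opens the same gap for a single patient with low baseline activity, from 14 to 17 lesions at the entry minimum. That range depends on the SD divisor and on how the two baseline lesions are spread. It also assumes that such a patient counts as low.

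A reader might want to go further and say how much more often the trial would be held under one rule than the other. The documents give no rate for these MRI events, and the two rules respond to different events, so no such probability can be supported. Nor is patient protection shown to fail, because the individual stops and the general safety clause remain in force.

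**What to change.** Adopt one MRI hold rule and word it identically in the synopsis and section 7.3.2. Either of two versions would do:

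- **(a)** State that item 2 is an immediate one-patient hold in addition to the five-patient rule. Do the same for item 1 if that is intended, with its patient count and a definition of low baseline activity.
- **(b)** Make items 1 and 2 individual dosing stops, with the trial held at five such discontinuations.

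In either case, state whether item 2 counts new Gd-enhancing lesions, and move item 3, with its DSMB discussion, to the individual rules. The cost is wording in the protocol and matching DSMB instructions. Visits, sample size and analysis are unaffected.
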